6.2. Endpoints

6.2.1. Primary Efficacy Endpoint

- Annualized rate of VOCs

VOC is defined as a documented episode of an acute painful crisis (for which there was not an explanation other than VOC) that involves moderate to severe pain lasting for at least 2 hours and at least one of the following:

- Use of escalated analgesia (including healthcare professional-instructed use of an analgesic prescription)

- A hospital, emergency department, or clinic visit and/or healthcare telephone consultation at the time of occurrence
- Diagnosis of ACS (defined as an acute illness characterized by fever and/or respiratory symptoms, accompanied by a new pulmonary infiltrate on a chest X-ray), hepatic sequestration, splenic sequestration, or priapism (in males)

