13.5.2.1 Derivation of Annualized Rate of VOCs

As described in Protocol Inclusion Criterion 3, a VOC is defined as a documented episode of acute painful crisis (for which there was not an explanation other than VOC) that involves moderate to severe pain lasting for at least 2 hours and at least one of the following:

- Use of escalated analgesia (including healthcare professional-instructed use of an analgesic prescription)
- A hospital, emergency department, or clinic visit and/or healthcare telephone consultation at the time of occurrence
- Diagnosis of acute chest syndrome (ACS) (defined as an acute illness characterized by fever and/or respiratory symptoms, accompanied by a new pulmonary infiltrate on a chest X-ray), hepatic sequestration, or splenic sequestration, or priapism (in males)

VOCs collected during the study are assumed to meet these criteria as well.

VOC information, including start and end date/time, primary setting for treatment (hospitalization/ emergency department, etc.), and treatments are collected on the "VOC" CRF page.

Annualized rate of VOCs is calculated as Total number of VOCs / ([Date of last dose of study drug– date of first dose of study drug + 1]/365.25).

Date of last dose of study drug is collected from the "End of Treatment" CRF page. If that date is not available (which is expected for some of the subjects in the IA), the data cut-off date will be used.

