13.5.4 Other Secondary Endpoints

Proportion of VOC-free subjects

VOC-free subjects are defined as these who did not experience a VOC after the first dose of study drug through the end of treatment. Proportion of VOC-free subjects will be analyzed using a stratified Cochran-Mantel-Haenszel (CMH) test adjusted for stratification factors of region (North America/Europe vs. Africa/Middle East) and HU use (Yes vs. No) using the ITT analysis set. Sensitivity analysis will be performed for proportion of VOC-free subjects using the PP analysis set.

Annualized rate of VOC-related hospitalizations

Annualized rate of VOC-related hospitalization is calculated as total number of VOC-related hospitalizations / ([Date of last dose of study drug – date of first dose of study drug + 1] / 365.25).

VOC-related hospitalization will be determined from the “Adverse Event” CRF when the AE’s preferred term = “sickle cell anaemia with crisis” and “Did the adverse event result in initial or prolonged hospitalization for the subject?” = “Yes”. Date of last dose of study drug are collected from “End of Treatment” CRF page. If that date is not available (which is expected for some of the subjects in IA), the data cut-off date will be used.

VOC-related hospitalization-free subjects are defined as these who did not experience a VOC-related hospitalization after the first dose of study drug through the end of treatment.

Analyses of annualized rate of VOC-related hospitalizations will be done in the same way as in [Section 13.5.2](#) as for the primary endpoint (annualized rate of VOCs).

Annualized rate of days hospitalized for VOC-related hospitalizations

Annualized rate of days hospitalized for VOC-related hospitalizations is calculated as (sum of total number of days hospitalized for VOC-related hospitalization / ([Date of last dose of study drug – date of first dose of study drug + 1] / 365.25)).

Number of days hospitalized for VOC-related hospitalization is calculated as the sum of (Date of Discharge – Date of Admission + 1) for all AEs with preferred term = “sickle cell anaemia with crisis” and “Did the adverse event result in initial or prolonged hospitalization for the subject?” = “Yes”.

Date of last dose of study drug are collected from “End of Treatment” CRF page. If that date is not available (which is expected for some of the subjects in IA), the data cut-off date will be used.

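### VOC-related hospitalizations are taken from a single AE preferred term, so an admission recorded only as ACS, sequestration or priapism is lost, and two crisis records for one stay are double counted

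*SAP*

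**What the plan says.** SAP 13.5.4 states that "VOC-related hospitalization will be determined from the" AE page of the CRF. A record qualifies on two conditions: its preferred term is "sickle cell anaemia with crisis", and the question "Did the adverse event result in initial or prolonged hospitalization for the subject" is answered Yes. For the days endpoint, "Number of days hospitalized for VOC-related hospitalization is calculated as the sum of (Date of Discharge – Date of Admission + 1) for all AEs" meeting the same two conditions. No rule covers records that overlap or share an admission.

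VOCs themselves come from another source. SAP 13.5.2.1 says that "VOC information, including start and end date/time, primary setting for treatment" and treatments given, is collected on a dedicated VOC page; hospitalization is one of the settings it names. A VOC there is an acute painful crisis "that involves moderate to severe pain lasting for at least 2 hours and at least one of the following": escalated analgesia, a healthcare contact, or a complication. Protocol 6.2.1 has the same definition, and its third feature is a diagnosis (ACS, "hepatic sequestration, splenic sequestration, or priapism (in males")). SAP 9.5 and 13.5.5 call VOCs with these diagnoses complicated VOCs.

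Protocol 6.2.4 names the endpoint as the annualized rate of hospitalizations for VOCs, with no restriction by preferred term. In SAP 12.3 and 12.4 the hospitalization rate is step 5 and the days rate step 6 of the testing order.

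**The concern.** The rule is narrower than the endpoint it is meant to deliver. A painful crisis with ACS, sequestration or priapism is a VOC and enters the primary endpoint through the VOC page. If the AE page records that admission only under the complication's term, it is not a VOC-related hospitalization. Nothing in the SAP sends those diagnoses to the crisis term or reconciles the two pages. The admissions at risk are those with complications.

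The days rule has a different fault, in the opposite direction. The flag covers both initial and prolonged hospitalization, so a second crisis AE that prolongs an existing stay also qualifies, and its days can be added on top of days already counted.

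The place in the testing order matters. Under SAP 12.4, once one null hypothesis is not rejected, all later p-values are nominal. If testing gets that far, mismeasurement at steps 5 and 6 also decides whether any later endpoint can be claimed. The same derivation feeds time to first VOC-related hospitalization (SAP 13.5.4) and the exploratory hospitalization counts (SAP 13.5.5).

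**Working it through.** The plan gives no assumed rate, sample size or power for the hospitalization endpoints, so there is no stated figure to reproduce. The check sets the two rules side by side and then works an illustration.

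**The same admission under the two rules**

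- *Painful crisis, AE term is the crisis term, flag Yes.* VOC page: a VOC. SAP 13.5.4: counted. The rules agree.
- *Painful crisis with ACS; both a crisis AE (flag Yes) and an ACS AE recorded.* VOC page: a VOC. SAP 13.5.4: counted once, because the filter drops the ACS record. The rules agree.
- *Painful crisis with ACS; only an ACS AE recorded.* VOC page: a VOC. SAP 13.5.4: not counted. The rules disagree.
- *One stay with two crisis AEs, both flagged.* SAP 13.5.4: the days of the stay are added twice. Whether step 5 counts one hospitalization or two is not stated.
- *ACS without a qualifying painful crisis.* Not a VOC under the definition. Leaving it out is correct.

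**Illustration for one subject (all values assumed)**

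Time on drug is 364 days, which is 364/365.25 = 0.9966 years. There are three VOC admissions: A, 7 days, one crisis AE; B, 10 days, a painful crisis with ACS recorded only as an ACS AE; C, 7 days, two crisis AEs for the same stay.

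- Days under SAP 13.5.4: 7 + 0 + (7 + 7) = 21, or 21/0.9966 = 21.07 per year.
- Days counted once per distinct VOC admission: 7 + 10 + 7 = 24, or 24/0.9966 = 24.08 per year.
- Admissions: the filter finds 2 distinct stays (2.01 per year) out of 3 (3.01 per year). If records are counted instead of stays, it returns 3, because the missed stay and the duplicate cancel.

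Totals can therefore look plausible while both errors are present.

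**Size of the undercount**

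Let *f* be the share of VOC admissions recorded only under another term. Ignoring double counting, measured rate = (1 − *f*) × true rate. For assumed *f* = 5%, 10%, 20% and 30%, this is 0.95, 0.90, 0.80 and 0.70 of the true rate.

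**Effect on the comparison**

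The ratio of mean rates (active to placebo) is multiplied by (1 − *f* active)/(1 − *f* placebo).

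- Equal shares, for example 10% and 10%: 0.90/0.90 = 1.00.
- 30% on active, 10% on placebo: 0.70/0.90 = 0.78, which favors active.
- 10% on active, 30% on placebo: 0.90/0.70 = 1.29, which goes against active.

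**The case against.** The strongest reply is that little may be lost in practice. Every complicated VOC must also be a painful crisis, so a site may well record a flagged crisis AE for the stay. Protocol 12.1.2.1.2 treats complications arising in hospital as AEs, which makes a crisis record plus a complication record a natural pattern, and that pattern is counted correctly. Coding conventions and CRF completion guidelines are not in these documents. This stands: the loss is conditional and its frequency is unknown.

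Four stronger readings are tempting, and the documents do not support them.

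- *ACS, sequestration or priapism is a VOC by itself.* The definition requires the painful crisis first.
- *Any two AE records for one admission are double counted.* Both must carry the crisis term. Summing over records adds days; it does not cause missed admissions.
- *An effect on ACS could not be seen.* SAP 13.5.5 plans summaries of complicated VOCs, ACS, priapism and sequestration, and time to first complicated VOC. SAP 13.5.8.1 tabulates serious AEs by preferred term.
- *The rate is understated by 10% to 30%.* That range is an assumption.

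It can also be said that the VOC page is no better as the only source. It records the primary setting, so a crisis treated mainly in an emergency department and then admitted could be missed. This also stands, and it shapes the remedy. None of it makes the written rule adequate: followed exactly, it omits some VOC admissions and can count some days twice.

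**Conclusion.** The point holds as a flaw in a stated rule. The single-term filter can exclude admissions that meet the trial's VOC definition, and the summation can double count days when crisis records share or overlap a stay. The first rests on the stay being recorded only under another term; the second on two flagged crisis records for the same stay. Neither frequency can be derived from the documents.

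The undercount equals whatever share is missed. The ratio of rates is biased only if that share differs between arms, for which the documents give no evidence either way. Steps 5 and 6, time to first VOC-related hospitalization and the exploratory hospitalization counts are affected. Time to first is exposed only to missed admissions, because a duplicate record does not move the date of the first. The primary endpoint and time to first VOC use the VOC page and are unaffected. The change should be made, but it does not threaten the trial's main conclusion.

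**What to change.** Amend SAP 13.5.4 before any unblinding, including that for the interim analysis.

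- **Event:** a VOC-related hospitalization is a VOC CRF event whose dates overlap a hospital admission recorded on the AE page under any preferred term. Do not rely on the primary-setting field alone. Alternatively, keep the AE-term approach and add the ACS, hepatic and splenic sequestration and priapism terms when they accompany a VOC CRF event.
- **Counting:** count each distinct admission once, and each calendar day in hospital once per subject.
- **Sensitivity:** keep the single-term derivation as a sensitivity analysis for steps 5 and 6.
- **Scope:** apply the definition to time to first VOC-related hospitalization and the exploratory counts.

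The cost is SAP wording and programming to link the VOC and AE pages. It uses the VOC dates and the admission and discharge dates on which the SAP already relies, so no new data collection is needed.

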12.4 Final Analysis

The database will be locked prior to the final analysis (FA) which will be conducted when all randomized subjects have reached Week 56 or terminated early. As described in [Section 12.3](#), all the efficacy endpoints will be tested in a hierarchical order, at the highest tolerated dose of IMR-687 vs placebo. If all the efficacy comparisons are successful, testing of the IMR-687 pooled dose vs. placebo, and of lower dose vs. placebo will be performed. Propagated alpha from the primary efficacy analysis at the IA will be used in the FA to maintain an overall type I error rate of 5% for 2-sided testing. After the first instance of a failure to reject the null hypothesis, p-values from all remaining comparisons will still be reported, but deemed nominal. The hierarchical order of testing of primary, key secondary and other secondary endpoints is:

1. Annualized rate of VOCs
2. Time to first VOC
3. HbF responder rate at Week 24
4. Proportion of VOC-free subjects
5. Annualized rate of VOC-related hospitalization
6. Annualized rate of days hospitalized for VOC-related hospitalizations
7. Time to second VOC
8. Change from baseline in key biomarkers of RBC hemolysis (indirect bilirubin and % reticulocytes) at Week 24 and Week 52
9. HbF responder rate at Week 52
10. Change from baseline in HbF (%) and F-cells (%) at Week 24 and Week 52
11. Hb responder rates at Week 24 and Week 52
12. Change from baseline in total Hb (g/dL) at Week 24 and Week 52
13. Change from baseline in other biomarkers of RBC hemolysis (absolute reticulocytes and lactate dehydrogenase [LDH]) at Week 24 and Week 52
14. Change from baseline in biomarkers of adhesion such as soluble E-selectin (E-sel), P-selectin (P-sel), intercellular adhesion molecule 1 (ICAM-1), and vascular cell adhesion molecule 1 (VCAM-1) at Week 24 and Week 52
15. Change from baseline in biomarkers of inflammation such as high-sensitivity C-reactive protein (hsCRP) and myeloperoxidase (MPO) at Week 24 and Week 52
16. Change from baseline in biomarkers of cardiac stress such as N-terminal prohormone of brain natriuretic peptide (NT-proBNP) at Week 24 and Week 52
17. Change from baseline in RBC indices, such as mean corpuscular volume (MCV) at Week 24 and Week 52
18. Change from baseline in each measured subdomain of ASCQ-Me questionnaire at Week 24 and Week 52
19. Change from baseline in total preference score and individual domain scores of PROPr questionnaire at Week 24 and Week 52

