13.5 Endpoint Analyses

13.5.1 Summary of Analyses

Primary efficacy endpoint, safety endpoints, secondary efficacy endpoints, and corresponding analysis methods are summarized in [Table 7](#) below. Exploratory analyses are detailed in [Section 13.5.5](#).

Table 7 Summary of Efficacy and Safety Analyses

| Endpoints | Analysis Time Points | Analysis Methods | Analysis Set | Time Point for analysis |
|--|---|--|--|-------------------------|
| Primary Efficacy • Annualized rate of VOCs | NA | Comparison of median differences among treatment groups using Stratified Wilcoxon rank-sum tests, with stratification factors of region and HU use. The van Elteren test may be used for the evaluation of treatment difference across strata. P-values for each active group (including pooled IMR-687) vs. placebo | ITT as primary analysis set, mITT, PP as sensitivity | IA, FA |
| Safety | NA | Descriptive statistics | Safety | IA, FA |
| Secondary Efficacy | | | | |
| • Time to first VOC • Time to second VOC | NA | Stratified log rank test, and stratified Cox regression model. p-values from a stratified log rank test and hazard ratios (with 95% CIs) estimated from a stratified Cox regression model with treatment arm and stratification factors of region and HU use as covariates will be provided for comparison of each active group (including pooled IMR-687) vs. placebo | ITT as primary analysis set, mITT, PP as sensitivity | IA*, FA |
| • Annualized rate of VOC-related hospitalizations • Annualized rate of days hospitalized for VOC-related hospitalizations | NA | Stratified Wilcoxon rank-sum tests, with stratification factors of region and HU use. P-values for each active group (including pooled IMR-687) vs. placebo | ITT as primary analysis set, mITT, PP as sensitivity | IA*, FA |
| • Proportion of VOC-free subjects • HbF responder rate at Week 24 and Week 52 • Hb responder rate at Week 24 and Week 52 | NA | Stratified CMH test adjusted for stratification factors of region and HU use. | ITT as primary analysis set, mITT, PP as sensitivity | IA*, FA |

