13.5.3.1 Time to first VOC

The time to first VOC event will be analyzed using Kaplan-Meier methods. Time in months to the first VOC event can be calculated as $([\text{date of first VOC event} - \text{date of first dose} + 1] / 30.4375)$.

Both start and end date of VOC event will be collected from “VOC” CRF page. The start date of the VOC is not expected to be missing and will be used for the analysis. In the rare event the start date is missing, then the end date can be used. If both start date and end date are missing, no imputation will be made and the event will be excluded from the analysis.

Subjects who experience no VOC events during the study will be censored at their study end date (or date cut-off date if the study end date is not available). Using the ITT set, the number and percentage of subjects with events (subjects who experienced at least 1 VOC on-study) and censored (subjects who did not experience any VOCs on-study) will be presented. The 25th, 50th (median), and 75th percentiles, along

with associated 2-sided 95% CIs based on the Brookmeyer and Crowley method will be presented. The p-values from a stratified log rank test and hazard ratios (and 95% CIs) estimated from a stratified Cox regression model with treatment arm and stratification factors (region and HU use) as covariates will be presented for comparison of each treatment group to placebo. Kaplan-Meier curves will be produced for the time to first VOC with separate curves for each treatment group.

Sensitivity analysis will be performed for Time to first VOC using the mITT and PP analysis sets. Major protocol deviations and subjects (or data) excluded from the PP analysis set will be defined by the Sponsor in a blinded manner prior to database lock. No imputation will be performed for the PP analysis.

13.5.3.2 Other sensitivity analyses may be added. All sensitivity analyses will be performed at FA.HbF responder rate at Week 24

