Annualized rate of days hospitalized for VOC-related hospitalization will be analyzed in the same way as annualized rate of VOC-related hospitalization.

Time to first for VOC-related hospitalization

The time to first VOC-related hospitalization event will be analyzed using Kaplan-Meier methods. Time in months to the first VOC-related hospitalization event can be calculated as ([date of first VOC-related hospitalization event – date of first dose + 1] / 30.4375).

Time to second VOC

This analysis of time to second VOC event will be analyzed using Kaplan-Meier methods similar to the analysis of the time to first VOC. A patient with less than two VOCs before withdrawal or completion of the study is considered censored at the time of withdrawal or completion of the study.

A sensitivity analysis will be performed separately, excluding these subjects without any VOCs.

HbF responder rate (as defined by proportion of subjects with an absolute increase of $\geq 3\%$ in HbF from baseline) at Week 52

This analysis of HbF responder at Week 52 will be similar to the HbF responder rate analysis at Week 24 ([Section 13.5.3.2](#)). Similar imputation rules will apply:

1. Subject will be treated as a non-responder if there is an initiation of HU post randomization and prior to Week 52.
2. HbF value from Week 36 (the last scheduled visit before the target analysis visit) will be used when Week 52 value is missing,
3. Any HbF value within 8 weeks (56 days) of RBC transfusion is excluded from all analyses.

Change from baseline in HbF (%) and F-cells (%) at Week 24 and Week 52

Change and percentage change from baseline in HbF (%) and F-cells (%) will be analyzed using mixed models for repeated measures (MMRM) with baseline value as a covariate, fixed effects for region (North America/Europe vs. Africa/Middle East), HU use (yes vs. no), treatment, visit, and treatment-by-visit interaction. Unstructured covariance matrices will be assumed for all models, but auto-regressive 1 (AR1) and compound symmetry (CS) may also be assessed (in that order) if the unstructured covariance matrix does not converge.

Values used at the visit and change from baseline for each parameter will be summarized for each post-baseline timepoint. The LS Mean estimates and 95% CIs will be displayed for all treatment groups. LS Mean difference estimates and 95% CIs with p-values for all IMR-687 treatment groups (relative to placebo) will be provided.

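### The time-to-second-VOC sensitivity analysis selects subjects on a post-randomization outcome, so it is not a randomized comparison and cannot speak to robustness (minor)

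*SAP*

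**What the plan says.** SAP section 13.5.4 defines the main analysis on all subjects: "A patient with less than two VOCs before withdrawal or completion of the study is considered censored". The method is borrowed: "This analysis of time to second VOC event will be analyzed using Kaplan-Meier methods similar to the analysis of the time to first VOC". The time-to-first-VOC text in section 13.5.3.1 counts months from first dose. Table 7 in section 13.5.1 asks for a stratified log-rank p-value and "hazard ratios (with 95% CIs) estimated from a stratified Cox regression model", with analysis sets given as "ITT as primary analysis set, mITT, PP as sensitivity".

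Section 13.5.4 then adds one more analysis: "A sensitivity analysis will be performed separately, excluding these subjects without any VOCs". It gives no rationale, no target quantity and no caution on interpretation.

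The same section makes freedom from VOCs an efficacy outcome: "VOC-free subjects are defined as these who did not experience a VOC after the first dose of study drug through the end of treatment". In the final testing order (section 12.4), time to first VOC is step 2, the VOC-free proportion is step 4, and "7. Time to second VOC" follows. No sensitivity analysis is a step.

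**The concern.** Whether a subject has any VOC is known only after treatment starts and depends on treatment if the drug works. Restricting to subjects with at least one VOC compares groups that randomization did not form. It also conditions on the future: a subject counts as at risk from first dose only because a VOC is seen later.

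The rule removes two kinds of subject: those followed to Week 52 without a crisis, and those who left early before having one. The second kind arises because Protocol section 8.5 withdraws from the study anyone who stops study drug. If the drug works and dropout is similar, both routes take a larger share of the drug arm.

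A sensitivity analysis should ask the same question under another plausible assumption. This one changes the population according to outcome. A weaker hazard ratio could come from selection alone and be misread as fragility of the main result.

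**Working it through.** **Inputs.** From SAP sections 8.0 and 8.1.2: 49 higher-dose and 31 placebo subjects, 5.0 versus 3.0 VOCs per year, SD 2.7, two-sided alpha 0.05, 25% dropout, 52 weeks of treatment. The SAP gives no hazard ratio or power for time to second VOC. Not in the documents, and so assumed: the count distribution (Poisson or gamma-Poisson) and exponential dropout. Stratum sizes are not given, so the models are unstratified.

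**The plan's own figure first.** The stated Wilcoxon power is reproduced by a two-sample noncentral t with each n multiplied by 3/π and rounded down, using the Appendix 7 difference 5.034 − 3 = 2.034 and SD 2.7.
- 31 and 49 become 29 and 46: power 0.880 (SAP: 0.88002).
- 24 and 37 become 22 and 35: power 0.776 (SAP: 0.77644).

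**Share with no VOC, without dropout.** Follow-up T = 364/365.25 = 0.9966 years.
- Poisson, exp(−μT): placebo exp(−4.983) = 0.7%; drug exp(−2.990) = 5.0%.
- Gamma-Poisson with SD 2.7 in each arm: shape k = μ²/(SD² − μ). Placebo 25/(7.29 − 5) = 10.9; drug 9/(7.29 − 3) = 2.1. Zero share (1 + μT/k)^(−k): placebo 1.7%, drug 15.6% (simulated 15.7%).

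**Effect of the exclusion.** VOC times were simulated. Time to second VOC ran from first dose, with censoring at dropout or Week 52. Hazard ratios are Cox estimates from 200,000 subjects per arm. Power is from 2,000 trials of 49 versus 31, log-rank at two-sided 0.05. Dropout is 25% in both arms.

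| Count model | No VOC, placebo / drug | Mean removed of 80 | HR kept → excluded | Power kept → excluded |
|---|---|---|---|---|
| SD 2.7 in each arm | 7.1% / 22.0% | 13.0 | 0.43 → 0.54 | 88% → 61% |
| Poisson | 5.9% / 12.1% | 7.8 | 0.48 → 0.52 | 82% → 74% |
| Gamma-Poisson, k = 2 in both arms | 13.7% / 22.5% | 15.3 | 0.60 → 0.66 | 47% → 34% |

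Arithmetic check, first row: 49 × 0.220 + 31 × 0.071 = 10.8 + 2.2 = 13.0 removed. Attenuation of the log hazard ratio: 1 − ln(0.537)/ln(0.426) = 27%. A second run of the Poisson case gave 0.47 → 0.51.

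**Direction.** With a working drug and equal dropout, the hazard ratio moved towards 1 in all nine scenarios run, and the log hazard ratio shrank by 9% to 27%. At SD 2.7 with 25% dropout, it moved up in 96% of simulated trials.

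**No drug effect (k = 2).** With equal dropout there is no shift (1.01 both ways). With unequal dropout the exclusion creates a shift of its own: 1.00 → 1.06 (drug 50%, placebo 10%) or 1.00 → 0.94 (drug 10%, placebo 50%).

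**Reversal.** With a working drug, k = 2, and extreme dropout (placebo 80%, drug 5%), the hazard ratio went from 0.58 to 0.56.

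**The case against.** The strongest reply is that nothing depends on this analysis. The main analysis keeps the VOC-free subjects, no sensitivity analysis is a testing step, and mITT and PP analyses of the same endpoint are also planned. That stands, and it sets the weight of the point.

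The size also depends heavily on the count model. The SAP's SD of 2.7 belongs to a normal-distribution power calculation. Imposing it on counts in both arms makes the drug arm far more dispersed (shape 2.1 against 10.9), which adds zeros there. With shape 10.9 in both arms, the hazard ratio moves only from about 0.51–0.52 to 0.55–0.56. This stands too, and is why a range is given.

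Four stronger readings are tempting, but the documents do not support them:
- *Only the drug's best responders are removed.* In the 25%-dropout simulations, about 46% (SD 2.7) to 69% (Poisson) of the excluded drug-arm subjects were dropouts. VOC-free placebo subjects go as well.
- *The analysis is biased against the drug by construction.* The direction depends on dropout and can reverse.
- *Its absence from Table 7 is a defect.* Table 7 is a summary. It also omits the negative binomial and tipping-point analyses of the primary endpoint.
- *The shift is from 0.37 to 0.50.* The approximation exp((O − E)/V) gives such values, but the SAP specifies a Cox model.

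The time origin is inferred too: section 13.5.4 only points to the time-to-first-VOC method and states no formula for the second event.

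None of this turns a comparison selected on outcome into a test of robustness.

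**Conclusion.** The point holds as a minor one. The planned sensitivity analysis conditions on a post-randomization outcome that the SAP counts as benefit, so its hazard ratio is not a randomized comparison. At the planning rates with 25% dropout in both arms, the hazard ratio moves towards 1 by 0.04 to 0.11, and power falls by 8 to 27 percentage points, depending on the count model. This rests on assumed count distributions, exponential dropout, unstratified models and time measured from first dose. Attenuation is the expected direction when dropout is similar between arms, but it is not certain.

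A reader might infer that step 7 of the hierarchy, the primary result or type I error control is compromised. They are not: the tested analysis retains all randomized subjects, and no decision rule uses this output.

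**What to change.** Delete the analysis as a sensitivity analysis. Alternatively, relabel it as a descriptive summary among subjects with a first VOC, with no treatment p-value, and state that it is not evidence on the robustness of the time-to-second-VOC result.

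Optionally, add a supplementary recurrent-event analysis of all ITT subjects with robust variance and the same strata. This targets the event rate rather than time to second VOC, and the negative binomial model in section 13.5.2.4 already covers much of that ground, so it is not required.

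The cost is a small SAP edit and the loss of one secondary output; no new data are needed. Make the change before the interim unblinding, because time to second VOC is also in the interim testing order (section 12.3).
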